**Table 2 Definition of Abnormal ECG Values by Parameter for Pediatric and Adolescent Subjects**

ECG parameter (unit)	Age (years old)	Abnormally Low	Abnormally High
HR (bpm)	6 to <8	<65	>115
	8 to <12	<55	>110
	12 to <16	<50	>105
	$\geq$ 16	<50	>100
PR interval (msec)	6 to <8	--	>160
	8 to <12	--	>175
	12 to <16	--	>180
	$\geq$ 16	--	>200
QRS interval (msec)	6 to <8	--	>100

	8 to <12	--	>105
	12 to <16	--	>110
	≥16	--	>120

## 2.6.7. Vital Signs, Weight, Waist Circumference, and BMI

Descriptive statistics (mean, SD etc.) will be provided for observed at the DB baseline, OL baseline, post-OL baseline visit, W52 endpoint, and endpoint, and change from DB baseline and OL baseline values, respectively of each vital sign parameters, weight, height, BMI, waist circumference listed below:

- Systolic blood pressure (SBP) in supine and standing positions
- Diastolic blood pressure (DBP) in supine and standing positions
- Heart rate in supine and standing positions
- Orthostatic change in SBP
- Orthostatic change in DBP
- Orthostatic change in heart rate
- Respiratory rate
- Temperature
- Body weight, height, BMI, and waist circumference,
- Age-and-sex specific z-scores of height and BMI (WHO)
- Age-and-sex specific z-score of weight (CDC)

WHO 2007 growth reference provides the reference information up to age of 19 years and 0 month while CDC 2000 growth chart provides the reference for United State subjects up to age of 20 years and 0 month. A small proportion of subjects in study 302 will reach 19 years old and a few subjects may reach 20 years old during in the extension study. For each subject, WHO 2007 growth reference at 19 years and 0 month will be used to derive the z-score and percentile of height and BMI for data collected after 19 years old; CDC 2000 growth chart at 20 years and 0 month will be used to derive the z-score and percentile of weight for data collected after 20 years old. For US subjects, CDC 2000 growth chart at 20 years and 0 month will be used to derive the z-score and percentile of height and BMI for data collected after 20 years old.

For analysis group and analysis subgroups A and C, WHO based z-scores and percentiles will be reported for height and BMI and CDC based z-score and percentile will be reported for weight. For analysis subgroup B and the output specific for US subjects, CDC based z-scores and percentiles of height, weight, and BMI will be summarized accordingly.

To better interpret these growth indexes, the expected value of height and BMI relative to DB baseline per WHO and the expected value of height, weight, and BMI relative to DB baseline per CDC at each open-label visits will be derived; corresponding changes in expected value from DB baseline will be generated as well. The number and percentage of subjects with weight status categories, defined as a value falling into the categories in Table 6.1 and Table 6.2, will be

summarized by analysis group and by analysis subgroup, respectively. This includes subjects having experienced at least one occurrence during the open-label extension study, up to and including endpoint.

**Table 6.1 Weight Status Categories for Pediatric and Adolescent Subjects per WHO Standard**

BMI (kg/m  )	Weight Status
< 3 th percentile	Underweight
3 th percentile ≤ BMI ≤ 85 th percentile	Normal
85 th percentile < BMI ≤ 97 th percentile	Overweight
> 97 th percentile	Obese

**Table 6.2 Weight Status Categories for Pediatric and Adolescent Subjects per CDC Standard**

BMI (kg/m  )	Weight Status
< 5 th percentile	Underweight
5 th percentile ≤ BMI ≤ 85 th percentile	Normal
85 th percentile < BMI ≤ 95 th percentile	Overweight
>95 th percentile	Obese

Shifts from OL baseline and shifts from DB baseline over time for weight status categories (Tables 6.1) will be summarized by analysis group to show the number and percentage of subjects that fall into above categories. A similar shift analysis will be done for US subjects (Table 6.2) by analysis subgroup D.

The number and percentage of subjects with Potentially Markedly Abnormal Vital Signs (PMAVS), defined in [Table 7](#), will be presented by analysis group at DB baseline and OL baseline (when applicable), post-OL baseline visits, W52 endpoint, endpoint, and in the first 52-weeks treatment period, and any treatment-emergent occurrence during the open-label treatment phase (the worst case).

**Table 7 Criteria for Potentially Markedly Abnormal Vital Signs for Pediatric and Adolescent Subjects**

Parameter (unit)	Age (years old)	Markedly Low	Markedly High
SBP (supine, standing) (mmHg)	6-12	Value ≤ 70 and ≥ 20 decrease from baseline	Value ≥ 120 and ≥ 20 increase from baseline
	13-18	Value ≤ 90 and ≥ 20 decrease from baseline	Value ≥ 135 and ≥ 20 increase from baseline
	≥ 19	Value ≤ 90 and	Value ≥ 180 and

		$\geq 20$ decrease from baseline	$\geq 20$ increase from baseline
DBP (supine, standing) (mmHg)	6-12	Value $\leq 40$ and $\geq 15$ decrease from baseline	Value $\geq 80$ and $\geq 15$ increase from baseline
	13-18	Value $\leq 50$ and $\geq 15$ decrease from baseline	Value $\geq 90$ and $\geq 15$ increase from baseline
	$\geq 19$	Value $\leq 50$ and $\geq 15$ decrease from baseline	Value $\geq 105$ and $\geq 15$ increase from baseline
Pulse rate (supine, standing) (bpm)	6-10	Value $\leq 60$ and $\geq 15$ decrease from baseline	Value $\geq 135$ and $\geq 15$ increase from baseline
	11-18	Value $\leq 50$ and $\geq 15$ decrease from baseline	Value $\geq 120$ and $\geq 15$ increase from baseline
	$\geq 19$	Value $\leq 50$ and $\geq 15$ decrease from baseline	Value $\geq 120$ and $\geq 15$ increase from baseline
SBP orthostatic criteria (mmHg)	$\sim$	$\geq 20$ decrease from supine to standing position	NA
DBP orthostatic criteria (mmHg)	$\sim$	$\geq 10$ decrease from supine to standing position	NA
Pulse rate orthostatic criteria (bpm)	$\sim$	NA	$\geq 20$ increase from supine to standing position
Temperature ( $^{\circ}$ C)	$\sim$	NA	Value $\geq 38.3^{\circ}$ C and $\geq 0.8^{\circ}$ C increase from baseline
Note: $\sim$ means that the abnormal range is applicable for all subjects; Baseline represents 'DB baseline' and 'OL baseline' respectively.			

A listing of subject data for those who satisfy MAPVS during the open-label study will be presented.

## 2.6.8. Young Mania Rating Scale (YMRS)

The YMRS is only applied to subjects who continued from Study D1050326.

The YMRS is an 11-item instrument used to assess the severity of mania in patients with a diagnosis of bipolar disorder. Ratings are based on patient self-reporting, combined with clinician observation. Seven items are rated on a 5-point scale, ranging from 0 to 4, and four items are rated on a 9-point scale, ranging from 0 to 8.

- Seven Items that are scored 0 to 4 are:
  - Elevated mood
  - Increased Motor Activity – Energy
  - Sexual Interest
  - Sleep
  - Language/Thought Disorder
  - Appearance
  - Insight
- Four items that are scored 0 to 8 are
  - Irritability

- Speech (Rate and Amount)
- Content
- Disruptive/Aggressive Behavior

The YMRS total score is the sum of the 11 individual items and ranges from 0 to 60. A higher score is associated with a greater severity of mania.

## **Analysis Methods**

### **Subjects continued from Study D1050326**

Summary statistics for the observed at the DB baseline, OL baseline, each post-OL baseline time point, W52 endpoint, and endpoint, change from DB baseline, and change from OL baseline in YMRS total score will be presented by analysis subgroup.

## **2.6.9. Extrapiramidal Symptoms Assessment Scales**

### **2.6.9.1. Barnes Akathisia Rating Scale**

The Barnes Akathisia Rating Scale (BARS) consists of four items: an objective rating (ranging 0 to 3), 2 subjective ratings of symptoms of akathisia (awareness of restlessness and reported distress related to restlessness: ranging 0 to 3), and a global clinical rating of akathisia, ranging from 0 (absent) to 5 (severe). The global rating score (item 4), that is scored separately, is the most relevant measure of severity of akathisia. Higher scores denote worsening akathisia. The subjective and objective items (items 1 through 3) are summed to yield a BARS total score with a range of 0 to 9. Higher values of the BARS total score indicate higher severity of akathisia.

### **For subjects continued from Studies D1050301 and D1050326**

Two items for subjective ratings of symptoms of akathisia (awareness of restlessness and reported distress related to restlessness) range from 0 to 3.

### **For subjects continued from Study D1050325**

Two items for subjective ratings of symptoms of akathisia (awareness of restlessness and reported distress related to restlessness) range from 0 to 3, and Not Applicable (NA). When any subjective rating is recorded as NA, the BARS total score will not be calculated and will be set as NA as well.

### **2.6.9.2. Abnormal Involuntary Movement Scale**

The Abnormal Involuntary Movement Scale (AIMS) contains items related to: facial and oral movements; extremity movements; trunk movements; global judgments and dental status. The individual items on the AIMS range from 0= ‘None’ to 4= ‘Severe’. Three other items assess the subject at a global level, and two items assess dental status. The individual items on the AIMS are rated from 0= ‘None’ to 4= ‘Severe’. The (non-global) total AIMS score is the sum of items 1 through 7 (ranging from 0 to 28). Items 8 through 12 will not be calculated in total AIMS

score. Higher values of the total AIMS score indicate increased severity in abnormal movement. The global severity score (Item 8) is the response to, “Severity of abnormal movements”, found within the global judgments section (0 - None, normal, 1 – Minimal, 2 – Mild, 3 – Moderate and 4 – Severe) and will be summarized separately.

#### 2.6.9.3. Simpson-Angus Scale

The Simpson-Angus Scale (SAS) is a clinician-rated assessment of neuroleptic-induced Parkinsonism consisting of 10 items. Items are anchor-based, rated on a 5-point scale (0-4), and address rigidity, gait (bradykinesia), tremor, glabellar tap, and salivation. Each individual item on the SAS ranges from 0= ‘Normal’ to 4= ‘Extreme Symptoms’. The SAS mean score is defined as the average of all 10 items and ranges between 0 and 4. Higher value of the SAS mean score indicates more severe condition of EPS symptom

SAS version 2 was to be used in studies D1050301, D1050325, D1050326, and D1050302. It was noticed on December 9, 2016 that all Hungarian sites in studies D1050301, D1050326, and D1050302 used SAS version 1 instead. There is no plan to update the SAS version for Hungarian sites; ie, Hungarian subjects will keep use SAS version 1 till the end of study D1050302.

The difference between SAS version 1 and version 2 is highlighted below:

Version 2	Version 1 (Hungarian Sites Only)
1. Gait	1. Gait
2. Arm dropping	2. Arm dropping
3. Shoulder shaking	3. Shoulder shaking
4. Elbow rigidity	4. Elbow rigidity
5. Wrist rigidity or fixation of position	5. Wrist rigidity or fixation of position
6. Head rotation	6. Leg Pendulousness
7. Glabella Tap	7. Head rotation
8. Tremor	8. Glabella Tap
9. Salivation	9. Tremor
10. Akathisia	10. Salivation

The SAS total score per V1 and V2 will be derived, separately. Since the SAS version related issue was found after the DBL of studies D1050301 and D1050326, DB baseline and OL baseline associated with these two SAS versions was derived and will be used in final analysis.

#### Analysis Methods

Summary statistics for the observed at the DB baseline, OL baseline, each post-OL baseline time point, W52 endpoint, and endpoint, change from DB baseline, and change from OL baseline in BARS total score, BARS global clinical assessment of akathisia score, AIMS total score, SAS 10-item mean score (all versions combined) will be presented by analysis group, and by analysis subgroup.

The post-OL baseline BARS global clinical assessment of Akathisia responses and the post-OL baseline AIMS global severity scores will be classified as ‘worsened’, ‘unchanged’, or ‘improved’, relative to a subject’s corresponding DB baseline response and OL baseline response, respectively. A higher post-OL baseline response than that of DB baseline or OL baseline would be classified as ‘worsened’ relative to DB baseline and OL baseline, respectively. Conversely, a lower value than that of DB baseline or OL baseline would be classified as ‘improved’, respectively. Frequency distribution over time of these variables will be summarized at each post-OL visit and endpoint by analysis group.

The AIMS total score at DB baseline, OL baseline, each post-OL visit, W52 endpoint, and endpoint will also be classified as ‘abnormal’ if either: at least two items have a response of ‘mild’ or higher; or at least one item has a response of ‘moderate’ or higher; otherwise, non-missing total scores will be classified as ‘normal’. This is a modification of the Schooler-Kane Criteria for Tardive Dyskinesia. The SAS 10-item mean score (all versions combined) at DB baseline, OL baseline, each post-OL visit, W52 endpoint, and endpoint will be classified as ‘abnormal’ if it exceeds 0.3; otherwise, non-missing mean scores will be classified as ‘normal.’ Shifts from OL baseline and shifts from DB baseline will be summarized for these variables (ie, abnormality status of the AIMS total score and the SAS 10-item mean score) at each assessed visit, endpoint, and overall for the open-label study up to and including endpoint (based on maximum severity) by analysis group.

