9.1.2. Concomitant Psychotropic Medications

Subjects may be treated with any approved benzodiazepines or antidepressants provided that the medications are not potent CYP3A4 inhibitors/inducers ([Appendix B](#)), during the course of the study, at the discretion of the investigator in a manner consistent with labeling recommendations and conventional medical practice. Monoamine oxidase inhibitors (MAOI) and additional antipsychotic medications (with the exception of lurasidone) will be prohibited.

Treatment with stimulants (provided that the medications are not potent CYP3A4 inhibitors/inducers), guanfacine or atomoxetine will be permitted during the course of the study for treatment of attentional deficits, at the discretion of the investigator in a manner consistent with labeling recommendations and conventional medical practice.

Treatment with benztropine (≤ 6 mg/day) will be permitted as needed for movement disorders. In cases where benztropine is not available, or a subject has had an inadequate response or intolerance to benztropine treatment, the following medications may be used to treat acute EPS: biperiden (≤ 16 mg/day) or trihexyphenidyl (≤ 15 mg/day) or diphenhydramine (≤ 100 mg/day for subjects entering from Study D1050301 or Study D1050326; ≤ 50 mg/day for subjects entering from Study D1050325). Treatment with propranolol (≤ 120 mg/day) will be

permitted as needed for akathisia. Medications used to treat movement disorders should not be given prophylactically.

Concomitant use of lorazepam, or equivalent benzodiazepine, is permitted at the discretion of the investigator (≤ 6 mg/day or equivalent dose) for intolerable anxiety/agitation, as clinically indicated. In regions where lorazepam or other specified medications are not available, another similar agent at equivalent doses will be permitted as specified by the Medical Monitor and/or the Operations Manual. Benzodiazepines administered orally or as a rapid acting IM injection should be used sparingly, and only when clinically required per investigator judgment. The date and time of last dose of lorazepam (or equivalent benzodiazepine) must be recorded at each visit. Subjects should be encouraged to avoid taking these medications within 8 hours prior to scheduled study assessments.

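### The BARS global akathisia rating has no worst-post-baseline summary, so akathisia that was rated and then resolved enters no ever-affected count from the scale, although akathisia adverse events are counted

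*SAP*

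**What the plan says.** SAP 2.6.9 (Analysis Methods) handles the three movement-disorder scales in two ways.

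- **BARS total and BARS global score.** These are summarised as continuous variables: "Summary statistics for the observed at the DB baseline, OL baseline, each post-OL baseline time point, W52 endpoint, and endpoint, change from DB baseline", and likewise change from OL baseline. The global score is also classed as worsened, unchanged or improved against each baseline, and "Frequency distribution over time of these variables will be summarized at each post-OL visit and endpoint by analysis group". The AIMS global severity item is classed and tabulated in the same way.
- **AIMS total and SAS mean.** Each is classed as normal or abnormal. Shifts in that status are shown "at each assessed visit, endpoint, and overall for the open-label study up to and including endpoint (based on maximum severity) by analysis group". A parenthesis limits the variables covered: "ie, abnormality status of the AIMS total score and the SAS 10-item mean score".

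SAP 2.1.7 lists the analyses that use an aggregated any-visit timepoint: laboratory values, vital signs, QTc and ECG. BARS is not among them. SAP 2.6.9.1 says that the BARS global item, scored 0 to 5, "is the most relevant measure of severity of akathisia". For subjects from D1050325 it adds: "When any subjective rating is recorded as NA, the BARS total score will not be calculated".

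**The concern.** Akathisia is a harm that the plan expects. BARS is rated at every visit after Day 1, Protocol 9.1.2 permits a medication for it ("Treatment with propranolol", as needed), and SAP 2.6.4 splits EPS-related adverse events into akathisia and non-akathisia. Protocol 7.1 also allows dose reduction for tolerability. These provisions matter here only because they mean that an episode may resolve while the subject stays in the study.

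A resolved episode appears in one or a few visit columns and is absent from the Week 52 endpoint and Endpoint, which are last-available values and not worst values. A reader of the BARS tables sees point prevalence and cannot tell how many subjects were ever rated as having akathisia, or how severe it became. In D1050325, a not-applicable subjective item removes the BARS total, so the global item may be the only usable BARS result for that subject. The SAP does not say how often this happens.

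**Working it through.** The plan gives no figure to reproduce. It is descriptive and sets no hypothesis (SAP 2.2.1). The check compares the text on each route and then asks what by-visit tables can yield.

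**1. Routes by which a BARS rating could enter a cumulative table**

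- *Maximum-severity shift, SAP 2.6.9:* limited to AIMS total and SAS mean status.
- *Aggregated timepoints, SAP 2.1.7:* BARS is not listed.
- *Visit windows, SAP 2.1.3:* one visit per window, the one closest to the target day, feeds the by-visit summaries. Other ratings in the window go to listings and to worst-case analyses, which are meant to ensure that all on-treatment measurements are used. BARS has no worst-case analysis. A rating at an additional visit can therefore reach Endpoint if it is the last, or a listing, but no ever-affected count.
- *Protocol 14.7.4.2:* descriptive statistics by scheduled visit for these scales.

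**2. Other sources of a cumulative count**

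- *Adverse events, SAP 2.6.4:* subjects with at least one akathisia event are counted. EPS-related events also get exposure-adjusted rates, and events are tabulated by exposure interval. This is a real cumulative count, but it depends on reporting. Adverse events come from non-leading questions (Protocol 11.1.2 and 13.1), and reported restlessness becomes akathisia only if the site confirms it. Neither document ties a BARS score to an adverse event entry.
- *SAS, SAP 2.6.9.3:* version 2 has one akathisia item; version 1, used at Hungarian sites, has none. Abnormal means a 10-item mean above 0.3. An isolated akathisia score of 3 gives 3/10 = 0.3, which does not exceed 0.3 and is classed as normal.
- *UKU, SAP 2.6.12:* summarised for any extension visit, but not collected in D1050325 (125 of 702 subjects). The documents do not name an akathisia item in it.

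**3. Can the ever-affected count be recovered from by-visit counts?**

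Inputs: N = 271 + 125 + 306 = 702 (Protocol 14.5; SAP 1.2.1). On-treatment BARS visits are V2E to V29E (Protocol Tables 3 to 5): Weeks 2, 4, 6 and 8, then every 4 weeks from 12 to 104, so 4 + 24 = 28.

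If x_v subjects are positive at visit v, the number ever positive lies between max(x_v) and min(N, Σx_v). With an assumed constant prevalence and no dropout:

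| Assumed prevalence per visit | Positive per visit | Lower bound | Upper bound |
|---|---|---|---|
| 1% | 7 | 7 | 7 × 28 = 196 |
| 2% | 14 | 14 | 14 × 28 = 392 |
| 5% | 35 | 35 | min(702, 35 × 28 = 980) = 702 |

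The same visit columns fit a few persistent cases or many brief ones. The prevalences are illustrative and not taken from the documents.

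**The case against.** The strongest reply is that akathisia already has a cumulative count. SAP 2.6.4 reports subjects with at least one event, by severity and action taken, and Protocol 13.2 requires new and worsening signs and symptoms to be recorded as adverse events. A transient, treated case should appear there. This stands. A reader might infer from the BARS tables alone that the plan never reports how many children developed akathisia; the documents do not support that. The gap is limited to scale-rated akathisia.

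The comparison with AIMS and SAS is also imperfect. Their overall shift rests on a defined normal/abnormal status, and the SAP sets no such cut-off for BARS. The closest counterpart, the AIMS global item, has the same by-visit limit as the BARS global item. This stands too, but a 0-to-5 shift table needs no cut-off, and AIMS still has an overall summary through its total score.

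Third, the SAP does not depart from the protocol. BARS is among the other safety variables (Protocol 14.4.2), with by-visit description promised. The point is therefore an improvement and not a correction of a breach. Listings hold all ratings, so the worst value could be extracted, but no summary table would show it.

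Finally, a worst-of-many-visits figure has its own bias. If a spurious one-point rise occurred at 1% of visits independently (assumed), 1 − 0.99^28 = 24.5% of subjects would count as ever worsened. This is a sound reason not to rely on an unthresholded count.

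**Conclusion.** The point holds in a limited form. The BARS global rating has no worst-post-baseline summary, and akathisia that was rated and then resolved, or was rated only at an additional or unscheduled visit, enters no cumulative count from the scale. Subjects who leave while akathisia is present do enter Endpoint. Akathisia adverse events are counted separately.

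It is tempting to attach a multiplier to the understatement. The documents give no incidence, duration or onset pattern for akathisia, so any multiplier would only return its assumptions. The bounds above run from no understatement, if the same subjects are affected throughout, to 28-fold at 1% or 2% prevalence, if each visit's cases are new. They show that by-visit tables cannot answer the question, not how wrong they are.

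This is a low-cost improvement to a safety summary in a study whose primary objective includes long-term safety. It is not a defect in the primary safety analysis.

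**What to change.** In SAP 2.6.9, extend the maximum-severity sentence to the BARS global clinical rating. Add a shift table from DB Baseline and, separately, from OL Baseline to the worst rating at any scheduled or unscheduled visit in the open-label treatment period, by analysis group.

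- Show all six categories (0 to 5) and do not rely on a bare count of subjects who ever rose by one point.
- State that the worst value is taken from ratings after OL Baseline. SAP 2.1.2 starts the open-label period at the OL Baseline visit itself for subjects previously on lurasidone.
- Place the table beside the akathisia adverse event incidence from SAP 2.6.4, so that rated and reported akathisia can be compared.

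The cost is one more descriptive table, from data already collected and with logic already needed for AIMS and SAS. The figure will look less favourable than the by-visit columns and can include rater noise, which the SAP already accepts for AIMS and SAS. Showing the severity categories lets the reader judge how much of it is a one-step change.
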